4.2.3 Rationale for Endpoints

A phase I trial of p53MVA was completed in patients with colorectal or pancreatic cancer. Patients with unresectable and chemotherapy resistant disease with over expression of p53 were eligible. The highest dose tested (5.6×10^8 pfu) was well tolerated. A robust CD8⁺ T cell responses against p53 were detected in the majority of patients after vaccination, but no clinical responses were apparent. We characterized patient peripheral blood T cells for expression of the Programmed Death 1(PD-1) receptor and found frequencies significantly higher than healthy controls. Furthermore, the percentage of PD1⁺ T cells and peak p53 response showed an inverse, statistically significant correlation in the CD8⁺ compartment. In light of our findings regarding PD-1 expression, *in vitro* blockade and p53 response, we believe that combining the vaccine with pembrolizumab is the logical next step in the optimization of p53MVA therapy for cancer. We therefore propose a phase II study to evaluate the efficacy and safety of pembrolizumab combined with the p53MVA vaccine in advanced ovarian cancer patients. The primary endpoint in this trial will be response rate (CR+PR). Secondary endpoints include median PFS, clinical benefit (CR+PR+SD>6 months), overall survival, safety and tolerability, and biological correlates which remain exploratory in nature

4.2.3.1 Efficacy Endpoints

Measurement of efficacy (primary endpoint) in this trial will be response rate (CR+PR).

Secondary endpoints will include median PFS, median OS and clinical benefit (CR+PR+SD lasting >6 months) and safety and tolerability. CR, PR and SD will be assessed according to irRECIST criteria (see Section 7.1.2.5)

5.0 METHODOLOGY

5.1 Study Population

5.1.1 Participant Inclusion Criteria

Participants are eligible to be included in the study only if all of the following criteria apply:

1. Female participants who are at least 18 years of age on the day of signing informed consent with histologically or cytologically confirmed diagnosis of epithelial ovarian, primary peritoneal or fallopian tube cancer will be enrolled in this study. Patients must have experienced recurrence or progression within 6 months after completion of platinum based chemotherapy (by RECIST 1.1 criteria).
2. A patient is eligible to participate if she is not pregnant (see Appendix 3), not breast-feeding, and at least one of the following conditions applies:
 - a.) Not a woman of childbearing potential (WOCBP) as defined in Appendix 3 OR
 - b.) A WOCBP who agrees to follow the contraceptive guidance in Appendix 3 during the treatment period and for at least 30 days after the last dose of study treatment.
3. The participant (or legally acceptable representative if applicable) provides written informed consent for the trial.
4. Have measurable disease based on RECIST 1.1, or detectable disease. Lesions situated in a previously irradiated area are considered measurable if progression has been demonstrated in such lesions.
 - a) Measurable disease is defined as at least one lesion that can be accurately measured in at least one dimension (longest dimension to be recorded). Each lesion must be greater than or equal to 10 mm when measured by CT, PET/CT or MRI. Lymph nodes must be greater than or equal to 15 mm in short axis when measured by CT, PET/CT or MRI.
 - Detectable disease in a patient is defined as one who does not have measurable disease, but has at least one of the following conditions:
 - * Baseline values of CA-125 at least 2 X ULN
 - * Ascites and/ or pleural effusion attributed to tumor
 - * Solid and/ or cystic abnormalities on radiographic imaging that do not meet modified RECIST criteria, immune-related response criteria (irRC) for target lesions.
- b) Platinum Resistance
 - Patients whose ovarian cancer recurs/progresses within 0-6 months following platinum-based chemotherapy have platinum resistant or refractory disease. These patients are not considered to benefit from additional platinum-based therapy and are treated with other sequential single agents. **Such patients are eligible for this trial.**
 - Patients with documented disease recurrence/progression within 6-12 months of completing platinum-based therapy, are considered to have 'borderline' platinum sensitivity. **These patients will not be eligible for this trial.**

- Patients who relapse more than 12 months after completion of platinum-based treatment are considered ‘platinum sensitive’ and **will not be eligible for this trial**, since they have a favorable (33-59%) chance of responding to further rounds of platinum based chemotherapy.

5. Patients with confirmed p53 mutation by molecular analysis and/or evidence of p53 overexpression by immunohistochemistry ($\geq 10\%$ of cells within the tumor staining positive) will be eligible. This will be assessed semi-quantitatively by a CLIA approved Pathology Core Pathologist, using CLIA approved mutational analysis or immunohistochemistry techniques on formalin-fixed paraffin-embedded tissue. In the case of equivocal IHC results, p53 involvement may be confirmed by detection of p53 molecular analysis on tumor DNA. Patients on whom molecular analysis of p53 mutations is already available, will not require ICH analysis. Molecular analysis may be performed as an additional research procedure at the end of the study (distinct from eligibility determination) if the PI deems it of scientific value and research funding is available to cover the cost. Patients are not required to have PD-L1 positive ovarian tumors and PD-L1 testing is not mandatory on this study. However, we will collect the data on PD-L1 testing when available.
6. Have an Eastern Cooperative Oncology Group (ECOG) performance status of ≤ 2 (Karnofsky $\geq 60\%$) and a life expectancy of at least 3 months.
7. Up to 4 prior chemotherapy regimens for recurrent disease are allowed. Adjuvant chemotherapy and maintenance Taxol after completion of six cycles of adjuvant Carboplatin – Taxol will not be counted as a “prior chemotherapy regimen” for the purpose of this study. Treatment with targeted agents or hormones would not be considered as a systemic chemotherapy regimen. Eligible Patients are those with documented disease recurrence/progression within 0-6 months of completing platinum-based chemotherapy. Patients should not have received any non-oncology, viral vaccines within 30 days prior to starting protocol treatment.
8. Have adequate organ function as defined in the following table (Table 1). Specimens must be collected within 14 days prior to the start of study treatment.

Table 1 Adequate Organ Function Values

System	Adequate Organ Function (Laboratory Value)
Hematological	
Absolute neutrophil count (ANC)	$\geq 1500/\mu\text{L}$
Platelets	$\geq 100\,000/\mu\text{L}$
Hemoglobin	$\geq 9.0\text{ g/dL}$ or $\geq 5.6\text{ mmol/L}^{\text{a}}$
Renal	
Creatinine OR Measured or calculated ^b creatinine clearance (GFR can also be used in place of creatinine or CrCl)	$\leq 1.5 \times \text{ULN}$ OR $\geq 50\text{ mL/min}$ for participant with creatinine levels $>1.5 \times$ institutional ULN
Hepatic	
Total bilirubin	$\leq 1.5 \times \text{ULN}$ OR direct bilirubin $\leq \text{ULN}$ for participants with total bilirubin levels $>1.5 \times \text{ULN}$
AST (SGOT) and ALT (SGPT)	$\leq 2.5 \times \text{ULN}$ ($\leq 5 \times \text{ULN}$ for participants with liver metastases)
Coagulation	
International normalized ratio (INR) OR prothrombin time (PT) Activated partial thromboplastin time (aPTT)	$\leq 1.5 \times \text{ULN}$ unless participant is receiving anticoagulant therapy as long as PT or aPTT is within therapeutic range of intended use of anticoagulants
Cardiac	
left ventricle ejection fraction (LVEF)	$\geq 55\%$
ALT (SGPT)=alanine aminotransferase (serum glutamic pyruvic transaminase); AST (SGOT)=aspartate aminotransferase (serum glutamic oxaloacetic transaminase); GFR=glomerular filtration rate; ULN=upper limit of normal.	
^a Criteria must be met without erythropoietin dependency and without packed red blood cell (pRBC) transfusion within last 2 weeks.	
^b Creatinine clearance (CrCl) should be calculated per institutional standard.	
Note: This table includes eligibility-defining laboratory value requirements for treatment; laboratory value requirements should be adapted according to local regulations and guidelines for the administration of specific chemotherapies.	

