17. Has a history or current evidence of any condition, therapy, or laboratory abnormality that might confound the results of the study, interfere with the subject's participation for the full duration of the study, or is not in the best interest of the subject to participate, in the opinion of the treating investigator.
18. Has known psychiatric or substance abuse disorders that would interfere with cooperation with the requirements of the trial.
19. Is pregnant or breastfeeding, or expecting to conceive children within the projected duration of the study, starting with the screening visit through 120 days after the last dose of trial treatment.
20. Patients with a history of cardiac disease are excluded: myocardial infarction or arterial thromboembolic events within 6 months prior to baseline, severe or unstable angina, New York Heart Association Class III or IV disease, QTcB (corrected according to Bazett's formula) interval >470 msec, serious uncontrolled hypertension (systolic >150 and/or

diastolic >100 mm Hg). Baseline electrocardiography, echocardiography and assessment of serum troponin (I) are included in the screening exams. Subjects in whom these assays are abnormal (EKG excluding 1st degree branch block, sinus bradycardia, sinus tachycardia or non-specific T wave changes, serum troponin \geq grade 2) are ineligible.

21. Patients with a family history or Li-Fraumeni syndrome will not be eligible.

22. History of severe environmental allergies or allergy to egg proteins.

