5.1.3.2 Contraception

Pembrolizumab may have adverse effects on a fetus in utero. Refer to Appendix 3 for approved methods of contraception.

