5.1.4 Pregnancy

5.1.4.1 Female participants:

Pregnancies and suspected pregnancies (including a positive pregnancy test regardless of age or disease state) of a female participant occurring after the participant receives the first dose of protocol therapy up to 120 days post-last dose of pembrolizumab are considered immediately reportable events or 30 days following cessation of treatment if the subject initiates new anticancer therapy, whichever is earlier. **Protocol therapy is to be discontinued immediately. The pregnancy, suspected pregnancy, or positive pregnancy test must be reported to the Study PI and the DCC immediately within 24 hours of awareness.** The female subject may be referred to an obstetrician-gynecologist (preferably one with reproductive toxicity experience) or another appropriate healthcare professional for further evaluation.

The Investigator should make every effort to follow the female participant until completion of the pregnancy per institutional policies, and should notify the Study PI.

Abnormal pregnancy outcomes and neonatal deaths that occur within 28 days of birth should be reported as an SAE per expedited reporting guidelines.

If a participant inadvertently becomes pregnant while on treatment with pembrolizumab, the participant will be immediately discontinued from study treatment. The site will contact the participant at least monthly and document the participant's status until the pregnancy has been completed or terminated. The outcome of the pregnancy will be reported to Merck within 2 working days if the outcome is a serious adverse experience (eg, death, abortion, congenital anomaly, or other disabling or life-threatening complication to the mother or newborn). The study

Investigator will make every effort to obtain permission to follow the outcome of the pregnancy and report the condition of the fetus or newborn to Merck.

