- All AEs meeting serious criteria, from the time of treatment start through 90 days following cessation of study treatment, or 30 days following cessation of study treatment if the participant initiates new anticancer therapy, whichever is earlier must be reported by the investigator.
- All pregnancies and exposure during breastfeeding, from the time of treatment start through 120 days following cessation of study treatment, or 30 days following cessation of study treatment if the participant initiates new anticancer therapy must be reported by the investigator.
- Additionally, any SAE brought to the attention of an investigator at any time outside of the time period specified above must be reported immediately by the investigator if the event is considered to be drug-related.

Investigators are not obligated to actively seek AE or SAE or other reportable safety events in former study participants. However, if the investigator learns of any SAE, including a death, at any time after a participant has been discharged from the study, and he/she considers the

event to be reasonably related to the study treatment or study participation, the investigator must promptly notify Merck.

7.3.1 Definition of an Overdose for This Protocol and Reporting of Overdose to the Sponsor and to Merck

For purposes of this study, an overdose of pembrolizumab will be defined as any dose of 1,000 mg or greater (≥ 5 times the indicated dose). No specific information is available on the treatment of overdose of pembrolizumab. In the event of overdose, the participant should be observed closely for signs of toxicity. Appropriate supportive treatment should be provided if clinically indicated.

If an adverse event(s) is associated with (“results from”) the overdose of a Merck product, the adverse event(s) is reported as a serious adverse event, even if no other seriousness criteria are met.

If a dose of Merck’s product meeting the protocol definition of overdose is taken without any associated clinical symptoms or abnormal laboratory results, the overdose is reported as a non-serious Event of Clinical Interest (ECI), using the terminology “accidental or intentional overdose without adverse effect.”

All reports of overdose with and without an adverse event must be reported within 24 hours to the Sponsor and within 2 working days hours to Merck Global Safety. (Attn: Worldwide Product Safety; [contact]).

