7.3.2 Reporting of Pregnancy and Lactation to the Sponsor and to Merck

Although pregnancy and infant exposure during breast feeding are not considered adverse events, it is the responsibility of investigators or their designees to report any pregnancy or lactation in a participant (spontaneously reported to them) that occurs during the study.

Pregnancies and infant exposures during breast feeding that occur after the consent form is signed but before treatment must be reported by the investigator if they cause the participant to be excluded from the trial, or are the result of a protocol-specified intervention, including but not limited to washout or discontinuation of usual therapy, diet, or a procedure.

Pregnancies and infant exposures during breast feeding that occur from the time of treatment start through 120 days following cessation of Sponsor’s product, or 30 days following cessation of treatment if the participant initiates new anticancer therapy, whichever is earlier, must be reported by the investigator. All reported pregnancies must be followed to the completion/termination of the pregnancy. Pregnancy outcomes of spontaneous abortion, missed abortion, benign hydatidiform mole, blighted ovum, fetal death, intrauterine death, miscarriage and stillbirth must be reported as serious events (Important Medical Events). If the pregnancy continues to term, the outcome (health of infant) must also be reported.

Such events must be reported within 24 hours to the Sponsor and within 2 working days to Merck Global Safety (Attn: Worldwide Product Safety; [contact]).

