Appendix 3: Contraceptive Guidance and Pregnancy Testing

Woman of Childbearing Potential (WOCBP)

A woman is considered fertile following menarche and until becoming post-menopausal unless permanently sterile (see below)

Women in the following categories are not considered WOCBP:

- Premenarchal
- Premenopausal female with 1 of the following:
 - Documented hysterectomy
 - Documented bilateral salpingectomy
 - Documented bilateral oophorectomy

Note: Documentation can come from the site personnel's review of the participant's medical records, medical examination, or medical history interview.

- Postmenopausal female
 - A postmenopausal state is defined as no menses for 12 months without an alternative medical cause.
 - A high follicle stimulating hormone (FSH) level in the postmenopausal range may be used to confirm a postmenopausal state in women not using hormonal contraception or hormonal replacement therapy (HRT). However, in the absence of 12 months of amenorrhea, confirmation with two FSH measurements in the postmenopausal range is required.
 - Females on HRT and whose menopausal status is in doubt will be required to use one of the non-hormonal highly effective contraception methods if they wish to continue their HRT during the study. Otherwise, they must discontinue HRT to allow confirmation of postmenopausal status before study enrollment.

Contraception Requirements

Female Participants:

Female participants of childbearing potential are eligible to participate if they agree to use a highly effective method of contraception that has a low user dependency consistently and correctly as described in Table 9 during the treatment phase and for 30 days after cessation of therapy.

Table 9 Highly Effective Contraceptive Methods That Have Low User Dependency

Highly Effective Methods That Have Low User Dependency Failure rate of <1% per year when used consistently and correctly.

 • Progestogen-only contraceptive implant ^a • Intrauterine hormone-releasing system (IUS) • Intrauterine device (IUD) • Bilateral tubal occlusion

 • Vasectomized partner A vasectomized partner is a highly effective contraception method provided that the partner is the sole male sexual partner of the WOCBP and the absence of sperm has been confirmed. If not, an additional highly effective method of contraception should be used.

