
 • Sexual abstinence Sexual abstinence is considered a highly effective method only if defined as refraining from heterosexual intercourse during the entire period of risk associated with the study treatment. The reliability of sexual abstinence needs to be evaluated in relation to the duration of the study and the preferred and usual lifestyle of the participant.

Notes:
 
Use should be consistent with local regulations regarding the use of contraceptive methods for participants of clinical studies.
 
a) If locally required, in accordance with Clinical Trial Facilitation Group (CTFG) guidelines, acceptable contraceptive implants are limited to those which inhibit ovulation.

Pregnancy Testing

WOCBP should only be included after a negative highly sensitive urine or serum pregnancy test. Pregnancy testing will be performed whenever an expected menstrual cycle is missed or when pregnancy is otherwise suspected.

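### Required contraception ends 30 days after the last dose, but exclusion 19 looks ahead to 120 days, so unplanned conception on days 31 to 120 is covered by no contraception requirement

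*Combined protocol and SAP*

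**What the plan says.** Two places in the combined protocol and SAP set a contraception duration, and they give the same number. Inclusion criterion 2b in Section 5.1.1 requires it "during the treatment period and for at least 30 days after the last dose of study treatment". The contraception requirements in Appendix 3, to which criterion 2b points, require it "during the treatment phase and for 30 days after cessation of therapy".

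Section 5.1.3.2 gives the reason and sends the reader to the same appendix: "Pembrolizumab may have adverse effects on a fetus in utero. Refer to Appendix 3 for approved methods of contraception".

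Other sections use 120 days:

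- Exclusion criterion 19 in Section 5.1.2 excludes women who are pregnant, breastfeeding or expecting to conceive over a period "starting with the screening visit through 120 days after the last dose of trial treatment".
- Section 5.1.4.1 makes pregnancies reportable "up to 120 days post-last dose of pembrolizumab are considered immediately reportable events or 30 days following cessation of treatment", the shorter limit applying when new anticancer therapy starts.
- Section 7.3 sets the reporting period "from the time of treatment start through 120 days following cessation of study treatment, or 30 days following cessation of study treatment", again shortened by new anticancer therapy.
- Section 7.3.2 has the same 120-day default, with the alternative of "30 days following cessation of treatment if the participant initiates new anticancer therapy, whichever is earlier, must be reported by the investigator".

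On testing, the flow chart in Section 6.1 shows a pregnancy test only at screening. After that, Appendix 3 says: "Pregnancy testing will be performed whenever an expected menstrual cycle is missed or when pregnancy is otherwise suspected".

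**The concern.** The protocol treats the 120 days after the last dose as a period in which a participant should not plan to conceive and in which, by default, a pregnancy must be reported. It requires her to prevent conception for only the first 30 of those days.

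Exclusion 19 deals with planned conception. It asks about expectation, it is an eligibility criterion, and the flow chart lists eligibility review only in the screening phase. It imposes no contraceptive method. Unplanned conception, which a contraception rule exists to prevent, is left uncovered from day 31 to day 120.

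At stake is fetal exposure to a drug that the protocol says may harm a fetus. A participant told 30 days could reasonably conclude that conception is acceptable from day 31. The trial's statistical conclusions are not at stake.

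**Working it through.** The plan gives no computed figure to reproduce. The check sets the post-treatment windows side by side and subtracts.

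| Provision | Where | Days after last dose | Shortened by new anticancer therapy? |
|---|---|---|---|
| Contraception | Section 5.1.1, criterion 2b | at least 30 | no |
| Contraception | Appendix 3 | 30 | no |
| Not expecting to conceive | Section 5.1.2, criterion 19 | 120 | no |
| Pregnancy reporting | Sections 5.1.4.1, 7.3, 7.3.2 | 120 | yes, to 30 |

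**Gap against exclusion 19.** 120 - 30 = 90 days, namely days 31 to 120. As a share of the window, 90 / 120 = 75%. Exclusion 19 has no shortening clause, so this gap is the same for every woman of childbearing potential.

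**Gap against pregnancy reporting.** By default, 120 - 30 = 90 days. If new anticancer therapy starts, the reporting window is min(120, 30) = 30 days and the gap is 30 - 30 = 0.

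**Could another provision cover days 31 to 120?**

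- *Safety follow-up visit (Section 7.1.5.3.1).* It takes place 1 to 3 weeks after the last dose, that is days 7 to 21, before required contraception ends.
- *Later follow-up (Sections 7.1.5.3.2 and 7.1.5.3.3).* Contacts are every 12 weeks, and 12 x 7 = 84 days. The imaging schedule also carries a parenthetical 42 ± 7 days, which is 35 to 49. If counted from the last dose, either timing falls within days 31 to 120. The content is imaging, disease status or survival status, and neither section mentions pregnancy or contraception.
- *Pregnancy testing.* After screening it depends on a missed period or suspicion, so it detects a pregnancy and does not prevent one.
- *Second course (Section 5.2.3).* The safety parameters in the eligibility criteria are checked again before retreatment. That applies only to women who restart, and it does not govern the period after their final dose.
- *Abstinence entry in Table 9.* It ties abstinence to the whole period of treatment-related risk, but only to define when abstinence counts as a method. It gives no number of days.

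None of these requires contraception after day 30.

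**Number affected.** Section 1.0 gives a total enrollment of 16 to 28. The documents do not say how many participants will be of childbearing potential, so the number lies between 0 and 28. Appendix 3 removes women with hysterectomy, bilateral salpingectomy, bilateral oophorectomy or menopause, so it is probably near the low end.

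**The case against.** The best defence is that the windows serve different purposes. The two contraception provisions agree with each other. Exclusion 19 is a statement of status and intent at entry, and the reporting window governs data collection. The documents state a fetal risk but give no duration for it, so they show a mismatch without proving that 120 is the right number. This is fair as far as it goes. It does not explain why the protocol would rule out planned conception until day 120 and leave unplanned conception unguarded from day 31, and no justification for 30 days is offered.

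A second point is practical. Most of the methods that Appendix 3 accepts (implant, intrauterine device or system, tubal occlusion, vasectomized partner) do not lapse on day 30 unless someone acts. Criterion 2b also sets a minimum, so longer use is allowed. Both facts narrow the gap in practice. Neither creates a requirement: a woman who has an implant removed on day 31 has complied fully.

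A third point is that the affected group may be very small or empty in this population, and the gap against the reporting window disappears when new anticancer therapy starts. Both stand and limit the practical importance. The protocol nevertheless provides expressly for women of childbearing potential, so its rule for them should be coherent.

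Finally, the consent pages were not available and may state a longer period. The finding is therefore limited to the protocol text that could be read.

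**Conclusion.** The concern holds. In the available text, contraception is required for 30 days after the last dose, while exclusion 19 and the default pregnancy-reporting window run to 120 days. The uncovered period is 90 days, three quarters of the protocol's own window, and no scheduled safeguard fills it.

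Taking 120 days as the target rests on the protocol's repeated use of that figure, because the documents give no washout or fetal-risk duration. The number of women concerned is unknown and probably small. This is a worthwhile participant-safety correction with no bearing on the primary endpoint, the two-stage design or its error rates.

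**What to change.** Replace 30 days with 120 days after the last dose of study treatment in inclusion criterion 2b and in the contraception requirements of Appendix 3, so that both match exclusion 19. Check that the consent form states the same period.

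The cost is one number changed in two places by amendment, and a contraception commitment 90 days longer for the probably few women of childbearing potential. The gap then falls from 90 days to 120 - 120 = 0. Endpoints, sample size and analysis stay as they are.
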